### Photo 1: Swab Sites (25)

**MEDICAL PROTOCOL (HRP-590)**

PROTOCOL TITLE: Effect of mechanical intervention on the scalp microbiome: setting the stage for the future management of cicatricial alopecias

VERSION DATE: 05 August 2023

To collect samples, sterile cotton swabs will be soaked for at least 30s in collection buffer (0.15 M NaCl, 0.1% Tween-20) and rubbed on the scalp surface in the following locations: right and left mid-frontal scalp, covering an area of 4 cm^2 per scalp section. Swabs will be stored in a collection buffer amended to a final concentration of 10% glycerol and stored at -80 °C prior to shipping/processing. If necessary, samples will be shipped to the microbiology lab on dry ice. Control swabs exposed to just room air and the buffer will be collected throughout the course of the study when treating participants. DNA will be extracted from the swab tips using the Daisy PowerSoil Pro DNA isolation kit (QIAGEN). Bacteria/archaea will be characterized by amplification and sequencing using the 515F/806R primer set targeting the V4 hypervariable region of the 16S rRNA gene. Fungal communities will be characterized by sequencing of the ITS1 region using the ITS1f/ITS2 primer set. Paired-end sequencing will be carried out at a read length of 300 bp on the Illumina MiSeq platform by the UMN Genomics Center. Bioinformatics and computational analyses of microbiome data will be done by the [name] lab using mothur software and raw data will be made publicly available on the Sequence Read Archive.

5.3 Study Duration: The total duration of participant participation will be approximately 2.5 weeks. The duration anticipated to enroll all study participants is expected to be approximately 5 months. It is anticipated that it will take just over 1 years to complete all study procedures including data analysis.

|  |   |
|--|---|
| Week 0 - Baseline/First Treatment | 

● Consenting and enrollment

● Demographic information

● Medical history

● Subjects to complete a questionnaire about current scalp care practices, skin type, and hair type, including:

○ Number of days prior to last shampooing

○ Names of products that they have used on their hair/scalp since their last shampoo (oils, sprays, gels, etc.)

○ Average frequency of shampooing per week

○ Average frequency of hair styling with hot tools per week

○ Hair type I-VIII (Loussouarn et al.)

○ Fitzpatrick Skin Type

 |
|--|---|

## MEDICAL PROTOCOL (HRP-590)

PROTOCOL TITLE: Effect of mechanical intervention on the scalp microbiome: setting the stage for the future management of cicatricial alopecias

VERSION DATE: 05 August 2023

|  |   |
|--|---|
|  | 

• Swab of right and left mid-frontal scalp prior to treatment

• HairMetrix photography before treatment

• Right side of scalp treatment with the Venus Glow™ device and brush (left side will not be treated)

• Swab of right mid-frontal scalp post- treatment

   |
| Beginning of Week 1 - Second Treatment
(+/- 3 days) | 

• Participant report of adverse events

• Swab of right and left mid-frontal scalp prior to treatment

• HairMetrix photography before treatment

• Right side of scalp treatment with the Venus Glow™ device and brush (left side will not be treated)

• Swab of right mid-frontal scalp post-treatment

 |
| End of Week 1- Final Visit (+/3 days)                   | 

• Participant report of adverse events

• Swab of right and left mid-frontal scalp

• HairMetrix photography

  |

All participants will have a final 3-6 day visit and swab collection after their treatments have been completed and they have returned to their typical hair and scalp care routine, described above. All visits including this final visit will be compensated at \$10 per visit. If a patient happens to miss a study visit, one of the study staff will reach out to the patient via a phone call.

5.4 Use of radiation: N/A

5.5 Use of Center for Magnetic Resonance Research: N/A

## 6.0 Data and Specimen Banking

6.1 Storage and Access: Deidentified data may be banked in the University's Box Secure Storage or REDCap database.

6.2 Data: Deidentified data may be banked for future analyses and compilation into larger datasets, such as clinical and demographic information and clinical assessments and rating scales.

## MEDICAL PROTOCOL (HRP-590)

PROTOCOL TITLE: Effect of mechanical intervention on the scalp microbiome: setting the stage for the future management of cicatricial alopecias

VERSION DATE: 05 August 2023

6.3 Release/Sharing: Deidentified data from this study may be used in the future to compile larger datasets from multiple studies with similar methodologies and populations to conduct additional analyses and publications. Should the investigators pursue this, future studies seeking to compile data acquired from this protocol will obtain IRB approval before doing so. In the event that this occurs, only investigators or study personnel listed in an IRB-approved protocol pertaining to the data compilation will have access to this data.

## 7.0 Sharing of Results with Participants

7.1 The individual results of the study will not be shared with participants or others. Deidentified data will be compiled, analyzed, and summarized for journal publication and/or poster presentations.

7.2 Sharing of genetic testing:

7.2.1 Disclosure of results: N/A

7.2.2 If returning results to participants: N/A

- Aggregate or individual results: N/A
- Laboratory results: N/A
- Plan for return of results to participants: N/A
- Types of results to be returned to participants: N/A

7.2.3 Future analysis of genotypes: N/A

## 8.0 Study Population

8.1 Inclusion Criteria:

Participants must meet all of the inclusion criteria.

- All individuals between 18-35 years of age
- Ability to understand study procedures and to comply with them

8.2 Exclusion Criteria:

All candidates meeting any of the exclusion criteria at baseline will be excluded from participation in this study.

- Non-English speakers
- Exclusion related to pregnancy, lactation, or has plans to become pregnant over the course of the study
  - Based on self-report from the participant
- Current scalp or hair disease diagnosis
- Using oral or topical antimicrobial medication 4 weeks prior to their baseline visit or in the duration of the study

## MEDICAL PROTOCOL (HRP-590)

PROTOCOL TITLE: Effect of mechanical intervention on the scalp microbiome: setting the stage for the future management of cicatricial alopecias

VERSION DATE: 05 August 2023

- Current clinical condition that, in the opinion of the site investigator, would interfere with adherence to study requirements
- Inability or unwillingness of individual to give written informed consent

8.3 Screening: Adult healthy subjects in the Department of Dermatology at the M Health Fairview Clinics and Surgery Center or M Health Fairview Maple Grove Clinic will be approached to determine their interest in the study. Dermatologists, [name] and [name], will identify healthy subjects that may benefit from scalp cleansing. The study will be introduced after the healthy subjects' clinical visit and contact information will be provided if they are interested. Participants may self-refer if they become aware of the study through recruitment materials or word of mouth referrals. Individuals who respond to the recruitment materials will be taken through a phone screening questionnaire. Interested healthy subjects will be screened for eligibility using the inclusion and exclusion criteria and written informed consent will be obtained from eligible healthy subjects at the baseline visit. Following the screening process, the healthy subjects will be seen for their baseline/first treatment visit (see section 5.3 for an outline of study procedures that occur at the baseline visit).

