### 1.0 Objectives

1.1 Purpose: The objective of this study is to assess the effect of standardized scalp care, specifically mechanical cleansing with the Venus Glow™ Device and water, on the scalp microbiome. This study also seeks to characterize the microbiome of the normal, healthy scalp, thereby providing a baseline for which the scalp affected by hair and scalp disease can be compared.

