#### 2.2 Preliminary Data:

Preliminary studies within our institution include a scalp swab assessment of participants with scarring alopecia compared to controls. The study thus far has found a predominance of *Staphylococcus*, *Propionibacterium*, and *Auritidibacter* in the frontal region of healthy control scalps. Additionally, one sample collected from a participant with dandruff had a greater proportion of *Staphylococcus* and a smaller proportion of *Propionibacterium* compared to samples, consistent with what has been reported in the literature (12,13,15,17).

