### 3.0 Study Endpoints/Events/Outcomes

- 3.1 Primary Endpoint/Event/Outcome: The primary endpoint will be scalp swab assessment of scalp microbiome composition before and after Venus Glow™ treatment. Our hypothesis is that there will be a decrease in microbe burden on the scalp with treatment.
- 3.2 Secondary Endpoint(s)/Event(s)/Outcome(s): Secondary endpoint includes scalp swab assessment of scalp microbiome composition after participants have returned to their normal hair and scalp care routine, providing information about the normal, healthy scalp microbiome. In addition, photography comparisons with the HairMetrix device will be taken before each treatment at the swab sites for each participant.

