## **11.0 Local Recruitment Methods**

*11.1 Recruitment Process:*

If a potential participant is identified at the Department of Dermatology at the University of Minnesota Clinics and Surgery Center or Maple Grove Clinic, the attending provider will briefly introduce the study and ask if a member of the study team may come in to talk with them. If the potential participant agrees, the investigator and/or study coordinator will describe the study in detail, answer any questions the potential participant may have and describe next steps. All investigators and study staff will be trained in privacy and confidentiality requirements for conducting research at Fairview facilities. Patients who have opted out of research in their medical record will only be approached by clinical staff.

Additionally, public recruitment will be done via the use of flyers in buildings on the University of Minnesota campus. These buildings could include academic buildings, student residences, athletic facilities, and student dining/recreation buildings. The study will also be posted on the University of Minnesota Department of Dermatology website:

<https://med.umn.edu/dermatology/research/clinical>. Additionally, we will attach a PDF of the flyer to email to be sent out to the Dermatology Interest Group listserv.

Participants may self-refer if they become aware of the study through these recruitment materials or word of mouth referrals. Individuals who respond to the recruitment materials will be taken through a phone screening questionnaire. If following the phone screen the potential participant is eligible and interested, the study coordinator will schedule the screening study visit.

*11.2 Identification of Potential Participants:* Potential participants will be identified by the investigators from among patients under their care. Investigators will make the initial contact with potential participants at the time of their clinic visit.

*11.3 Recruitment Materials:* Public recruitment will be done via the use of flyers that include the study and contact information. Tabs will be available at the bottom of the flyer to take if interested. Flyers will be posted in buildings on the University of Minnesota campus. These buildings could include the Malcolm Moos Health Sciences Tower, Phillips-Wangensteen building, Molecular and Cellular Biology building, and Jackson Hall.

*11.4 Payment:*

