## **14.0 Potential Benefits to Participants**

*14.1 Potential Benefits: Participants may experience an improvement in scale and/or oiliness of the scalp. Additionally, society and investigators will benefit from the knowledge gained.*

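### Section 8.3 has clinic dermatologists pick healthy people who may benefit from scalp cleansing, which does not fit the aim of describing the normal, healthy scalp as a reference

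*Combined protocol and SAP*

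**What the plan says.** Section 1.1 gives the study a second purpose beside the device question: to "characterize the microbiome of the normal, healthy scalp, thereby providing a baseline" against which diseased scalps can later be compared. Section 3.2 ties the secondary swab endpoint to it, as "providing information about the normal, healthy scalp microbiome".

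Section 8.1 asks for an age range and the ability to understand and comply. In section 8.2 the only exclusion about the state of the scalp is "Current scalp or hair disease diagnosis". Section 5.1 likewise defines healthy participants as people without such a diagnosis.

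Section 8.3 (Screening) then says that dermatologists at the clinics "will identify healthy subjects that may benefit from scalp cleansing". It gives no criteria for that judgement. The only clinical benefit to participants that the protocol describes is in section 14.1: "Participants may experience an improvement in scale and/or oiliness of the scalp".

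There are two recruitment routes. Sections 8.3 and 11.1 allow self-referral through flyers, the department website, a listserv and word of mouth. Section 11.2 mentions the clinic route alone: "Potential participants will be identified by the investigators from among patients under their care". No split between the routes is given.

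**The concern.** A reference for the normal scalp should come from people chosen only because they are healthy. The clause in section 8.3 adds a second reason for choosing them, and that reason may be related to what is measured. If the dermatologist's idea of benefit is less scale or oil, the clinic route favours people who have visible scale or oil but no diagnosis.

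The protocol's own background makes this relevant. Section 2.2 reports that "one sample collected from a participant with dandruff had a greater proportion of" Staphylococcus, and several studies tabulated in section 2.3 report the same for dandruff. A reference enriched for such scalps would not represent the ordinary healthy scalp, and later comparisons with disease would inherit the distortion. With 20 to 25 participants planned (section 5.1), a handful of such recruits could matter.

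**Working it through.** The plan states no figure on this point, so the check is mainly a reading of the sections against each other.

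**1. Is the step additional to eligibility?** Yes, as written. Sections 8.1 and 8.2 contain no benefit criterion, and neither do 11.1 and 11.2. It appears only in section 8.3.

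**2. Could undiagnosed scale or oiliness enter?** Yes. Section 8.2 excludes a current diagnosis, not the sign itself.

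**3. Would the plan detect it?** Not as written. The visit schedule in section 5.3 lists neither recruitment route nor a grade for scale or oiliness. HairMetrix images and shampoo history are collected, but no section says that the images are scored for scale. Section 15.1 names sex and skin type as example factors, not route.

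**4. Is the trait linked to the outcome in the protocol's own evidence?** Section 2.3 tabulates eight comparisons involving dandruff:

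| Finding in dandruff | Raised or lowered | Non-significant change | No difference or not reported |
|---|---|---|---|
| More Staphylococcus | 5 | 1 | 2 |
| Less Propionibacterium (Cutibacterium) | 4 | 1 | 3 |

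The Staphylococcus link is fairly consistent, and the Propionibacterium evidence is mixed. Section 2.2 adds one sample. No section reports a microbiome shift for oiliness.

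**5. Which way would later comparisons move?** The section 2.3 study that included lichen planopilaris (LPP) and frontal fibrosing alopecia (FFA) reports more Staphylococcus in lesions. Against that pattern, a reference with raised Staphylococcus would shrink the apparent difference. A comparison of alopecia areata with healthy controls reports more P. acnes and less S. epidermidis; against that pattern the same reference would widen the difference. The LPP/FFA study also had an alopecia areata group and reports raised Staphylococcus in lesions of all its alopecia participants, so the direction for alopecia areata is not settled.

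**6. How large could it be?** Two inputs are missing: the share *s* recruited through the clinics, and the shift *d* (in SD units) of that group's mean from the ordinary healthy mean. Both are assumed here.

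- Number selected this way, for *s* from 25% to 75%: 0.25 × 20 = 5, and 0.75 × 25 = 18.75, about 19. These are counts of recruits, not of bias.
- Bias of the reference mean = *s* × *d*. Standard error of the mean = 1/√n, which is 0.224 SD at n = 20 and 0.200 SD at n = 25.

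| Assumed s | Assumed d | Bias (SD) | In SE, n = 20 | In SE, n = 25 |
|---|---|---|---|---|
| 25% | 0.2 | 0.05 | 0.22 | 0.25 |
| 50% | 0.5 | 0.25 | 1.12 | 1.25 |
| 75% | 0.5 | 0.375 | 1.68 | 1.88 |
| 100% | 0.8 | 0.80 | 3.58 | 4.00 |

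The range, from negligible to dominant, reflects the assumptions and is not an estimate.

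**The case against.** The best case for the plan is that the clause is loose recruitment wording, not a gate. The sentence before it says that healthy adults in the clinics will be approached, with no benefit filter. A later sentence says that they are screened on the inclusion and exclusion criteria, and sections 11.1 and 11.2 describe clinic recruitment without the clause. No section says that benefit in 8.3 means what 14.1 describes. Dermatologists told to find healthy subjects are also well placed to recognise dandruff, so undiagnosed scaling might enter more easily through self-referral and a phone questionnaire.

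Much of this stands. The link to section 14.1 is an inference, though a natural one. The text says may benefit, so a reader who infers that people are chosen because benefit is likely, or that the sample is shown to be biased, goes further than the documents. The diagnosis-only exclusion applies to both routes. But the clause remains in the current text as an undefined selection step, and nothing in the plan limits or records its effect.

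A reader might also infer that the device result is biased. The documents do not support that: the primary analysis in section 15.1 compares treated and untreated portions of the same scalps, so how people were selected does not threaten its internal validity. That the device effect would be larger in these people is speculation. Nor do the documents say which genera later disease comparisons will use; section 15.1 refers only to about 20 pre-specified bacteria, without naming them.

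**Conclusion.** The point holds as a mismatch between a recruitment rule and a stated aim. Section 8.3 adds a selection step that the eligibility criteria lack and that can enrich the normal-scalp reference for undiagnosed scaly or oily scalps. This rests on two assumptions: that the clause is applied in practice, and that benefit is read as in section 14.1. Given both, a shift toward more Staphylococcus is the best-supported direction. A reader might infer that the reference would understate the difference from diseased scalp in general. The documents support that for LPP and FFA only; for alopecia areata the distortion could run the other way.

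The size is not quantifiable from the documents, and self-referral may reduce it. What is at stake is the descriptive aim in sections 1.1 and 3.2 and the generalizability of the device result. The change is worth making because it is nearly free, not because serious bias has been shown.

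**What to change.** In section 8.3, end the phrase quoted above after the word subjects, deleting the clause about benefit, so that clinic recruits are approached on sections 8.1 and 8.2 alone. Add one field recording recruitment route (clinic or self-referral), and describe the baseline microbiome profile by route. Label this a descriptive check: with 20 to 25 people the subgroups are small, route is only a proxy for scalp condition, and similar profiles would not show absence of bias. If enrolment is already under way, route can still be recorded and reported.

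The cost is one deleted clause, one form field and slightly less targeted clinic recruitment. Visits, treatment and the primary analysis do not change. The fix does not keep undiagnosed scaling out of the sample, because the exclusion still turns on a diagnosis for both routes; it removes only the avoidable reason for selecting it.

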## 9.0 Vulnerable Populations

### 9.1 Vulnerable Populations:

| Population / Group   | Identify whether any of the following populations will be targeted, included (not necessarily targeted) or excluded from participation in the study. |
|--|--|
| Children   | No   |
| Pregnant women/fetuses/neonates  | No   |
| Prisoners  | No   |
| Adults lacking capacity to consent and/or adults with diminished capacity to consent, including, but not limited to, those with acute medical conditions, psychiatric disorders, neurologic disorders, developmental disorders, and behavioral disorders | No   |
| Non-English speakers   | No   |
| Those unable to read (illiterate)  | No   |
| Employees of the researcher  | No   |

**MEDICAL PROTOCOL (HRP-590)**

PROTOCOL TITLE: Effect of mechanical intervention on the scalp microbiome: setting the stage for the future management of cicatricial alopecias

VERSION DATE: 05 August 2023

|   |                         |
|---|-------------------------|
| Students of the researcher  | No                      |
| Undervalued or disenfranchised social group   | Included / not targeted |
| Active members of the military (service members), DoD personnel (including civilian employees)  | Included                |
| Individual or group that is approached for participation in research during a stressful situation such as emergency room setting, childbirth (labor), etc.                    | No                      |
| Individual or group that is disadvantaged in the distribution of social goods and services such as income, housing, or healthcare.  | Included / not targeted |
| Individual or group with a serious health condition for which there are no satisfactory standard treatments.  | No                      |
| Individual or group with a fear of negative consequences for not participating in the research (e.g. institutionalization, deportation, disclosure of stigmatizing behavior). | No                      |
| Any other circumstance/dynamic that could increase vulnerability to coercion or exploitation that might influence consent to research or decision to continue in research.    | No                      |

**9.2 Additional Safeguards:** Undervalued or disadvantaged people may not be known, research staff will not be asking a direct question about socioeconomic status to potential participants. We do not anticipate the vulnerability for this group to be increased by participating in this study. Additionally, members of the military may not be known, as research staff will not be asking a direct question about military status to potential participants. We do not anticipate the vulnerability for this group to be increased by participating in this study.

**10.0 Local Number of Participants**

## MEDICAL PROTOCOL (HRP-590)

PROTOCOL TITLE: Effect of mechanical intervention on the scalp microbiome: setting the stage for the future management of cicatricial alopecias

VERSION DATE: 05 August 2023

*10.1 Local Number of Participants to be Consented:* 40 participants are needed for data analysis and we anticipate needing to consent 55 people to reach that goal.

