## 12.0 Withdrawal of Participants

- 12.1 Withdrawal Circumstances: Participation in this study is voluntary. Participants are free to withdraw at any time. Investigators may also withdraw participants from the study if participants fail to adhere to the study protocol requirements. Possible withdrawal circumstances may also include: the participant no longer meets the inclusion/exclusion criteria, the participant is lost to follow-up, or it is in the participant's best interest to withdraw from the study, as determined by the PI.
- 12.2 Withdrawal Procedures: Data collection of withdrawn participants will be collected up to the point of withdrawal. Data from withdrawn participants will not be included in the analysis.
- 12.3 Termination Procedures: This study may be suspended or prematurely terminated if there is sufficient reasonable cause. If the study is prematurely terminated or suspended, the PI will promptly inform the IRB and will provide the reason(s) for the termination or suspension. The study team will also notify the participants of the study termination. Data will not be used after termination. Circumstances that may warrant termination or suspension include, but are not limited to:
  - Determination of unexpected, significant, or unacceptable risk to participants
  - Demonstration of efficacy that would warrant stopping
  - Insufficient compliance to protocol requirements
  - Data that are not sufficiently complete and/or evaluable
  - Determination of futility

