## **15.0 Statistical Considerations**

*15.1 Data Analysis Plan:*

The primary analysis will evaluate whether there is a difference in the baseline and 2-week change in the relative abundance of pre-specified bacteria (approx. 20) between the device-treated portion of the scalp and the non-treated portion. In order to account for the within-subject correlation, mixed-effects models will be performed. As a secondary analysis, we will compare the HairMetrix images and analyze how various demographic and clinical factors such as sex and skin type impact the effect of the device.

*15.2 Power Analysis:*

Limited data are available to inform a power/sample size estimate. However, if there is a total of 38 subjects (40 initial, with 5% dropout), then we will have pre- and post-treatment data for 38 device-treated, and 38 non-treated portions of the scalp. Even when ignoring the within-subject correlation, this will allow us to have 80% power to detect an effect size of 0.7 (difference in the baseline to week 1 change between groups), assuming an alpha of 0.05.

*15.3 Data Integrity:*

- The study monitor will ensure that the investigation is conducted according to protocol design and regulatory requirements. The monitor will provide ongoing monitoring of data validity and regulatory issues (e.g., eligibility determinations, consent form process, serious adverse event reporting, IRB actions, disclosures of conflict of interest).
- Study records will be monitored at regular intervals by the study monitor. The monitor will perform source data verification and as such must be given access to the subject's primary source documentation, such as paper or electronic medical records such as consent to participate in the study, visit dates, demographic information, adverse events, concomitant medications, drug accountability, etc. that support data entries in the CRF.

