22.2 International Research: N/A

## 23.0 Multi-Site Research: N/A

## 24.0 Coordinating Center Research

24.1 Role: N/A

24.2 Responsibilities: N/A

24.3 Oversight: N/A

24.4 Collection and Management of Data: N/A

## 25.0 Resources Available

25.1 Resources Available:

- The dermatology research interns/fellows will be participating in study procedures with the support of the PI. No students will be involved in this study.
- The number of recruitable participants is appropriate for the time period of three years. Forty participants are needed for data analysis and we anticipate needing to consent 55 people to reach that goal.
- One to two hours of PI/study staff time will be dedicated to each visit.
- Facilities for this study include the M Health Fairview Maple Grove Clinic, M Health Fairview Clinics and Surgery Center, and the clinical research room in the University of Minnesota Department of Dermatology.
- There are no anticipated severe consequences of the treatment, however, two of the sites are in the clinical setting and one is connected to the UMMC Hospital.
- The PI or Co-PI will be present for all treatments, in addition to dedicated dermatology research staff.

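### Sections 10.1, 15.2 and 25.1 use 40 in two senses with unreconciled loss rates (27% and 5%), and 15.2's 38 analysed and its power cannot be reached under the cap of 25 in 5.1

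*Combined protocol and SAP*

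**What the plan says.** - **Section 10.1:** "40 participants are needed for data analysis and we anticipate needing to consent 55 people to reach that goal". Section 25.1 says the same: "Forty participants are needed for data analysis and we anticipate needing to consent 55 people to reach that goal". Here 40 is the number analysed. Neither section explains why 15 people are lost, and neither calls the loss dropout.
- **Section 15.2:** the calculation applies "if there is a total of 38 subjects (40 initial, with 5% dropout"), giving "pre- and post-treatment data for 38 device-treated, and 38 non-treated portions of the scalp". Here 40 is the number starting. The claim is "80% power to detect an effect size of 0.7", "assuming an alpha of 0.05", with the within-subject correlation ignored.
- **Section 12.2:** "Data from withdrawn participants will not be included in the analysis".
- **Section 5.1:** total enrolment is 20-25, with an upper limit of 25. The Revision History shows that this came in with the August 2023 revision, whose listed changes are all on page 10. Sections 10.1, 15.2 and 25.1 still carry the larger numbers.
- **Sections 8.3 and 5.3:** written consent is taken at the baseline visit from people already found eligible, and consent, enrolment and first treatment share the Week 0 visit.

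**The concern.** The number 40 is an analysed count in two sections and a starting count in a third, and the losses attached to it differ by a factor of more than five. Because 12.2 excludes everyone who withdraws, each loss after the start lowers the analysed number directly, so the power statement depends on which rate applies. With eligibility checked before consent and treatment given at the same visit, there is limited room for 15 people to disappear before treatment.

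At stake is whether 15.2 describes the trial now planned. With at most 25 enrolled it does not. If 15.2 were updated for 20-25 but kept 5% without explanation, the new figure would still rest on a loss rate that 10.1 and 25.1 do not support.

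**Working it through.** **Inputs.** 55 consented and 40 analysed (10.1, 25.1); 40 initial, 5% dropout, 38 analysed, effect size 0.7, alpha 0.05, correlation ignored (15.2); 20-25 enrolled (5.1). Sidedness is not stated, so I assume two-sided. The effect size is taken as a standardised difference (SD = 1).

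**Step 1: the two loss rates.**
- 10.1 and 25.1, consent to analysis: 1 - 40/55 = 15/55 = 27.3%.
- 15.2, start to analysis: 1 - 38/40 = 5.0%.
- The denominators differ. Chained as 55 to 40 to 38, the overall loss is 1 - 38/55 = 30.9%.

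**Step 2: reproduce 15.2.** 40 x 0.95 = 38, as stated. For a two-sample t-test with n per group, the noncentrality is d x sqrt(n/2) on 2n - 2 degrees of freedom. At n = 38 and d = 0.7 it is 0.7 x sqrt(19) = 3.05, which gives 85% power. The effect detectable with 80% power at n = 38 is 0.651, which rounds to 0.7. The sentence in 15.2 is therefore rounded or conservative for 38 analysed, not overstated.

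**Step 3: apply both rates to 5.1.**
- 5% loss: 20 x 0.95 = 19; 25 x 0.95 = 23.75, so 23 or 24.
- 27.3% loss: 20 x 40/55 = 14.5, so about 15; 25 x 40/55 = 18.2, so 18.

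**Step 4: power on 15.2's unpaired basis (effect 0.7, two-sided 0.05, t-test).**

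| Enrolled | Loss | Analysed | Power | Detectable effect at 80% power |
|---|---|---|---|---|
| 40 (15.2) | 5% | 38 | 85% | 0.65 |
| 25 | none | 25 | 68% | 0.81 |
| 25 | 5% | 24 (23) | 66% (64%) | 0.83 (0.85) |
| 25 | 27% | 18 | 53% | 0.96 |
| 20 | none | 20 | 58% | 0.91 |
| 20 | 5% | 19 | 56% | 0.93 |
| 20 | 27% | 15 | 46% | 1.06 |

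Rounding 14.5 down to 14 would give 43%.

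**Step 5: separate the two causes.** At 25 enrolled and 5% loss, power falls from 85% to 66%, which is 19 points due to the enrolment cut. Moving from 5% to 27% loss takes it from 66% to 53%, a further 13 points. At 20 enrolled the two steps are 29 points (85% to 56%) and 10 points (56% to 46%).

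**Step 6: allow for pairing.** The protocol gives no within-subject correlation, so I show a range. With correlation r between the changes on the two sides, the paired effect is 0.7/sqrt(2(1 - r)) on n - 1 degrees of freedom.

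| Analysed | r = 0 | r = 0.3 | r = 0.5 |
|---|---|---|---|
| 15 | 43% | 57% | 71% |
| 18 | 51% | 66% | 80% |
| 19 | 53% | 68% | 82% |
| 24 | 64% | 79% | 91% |

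**The case against.** The strongest reply is that the two rates measure different things: 55 consented, 40 starting, 38 completing. This stands as a possibility. Section 11.1 refers to a screening study visit after the phone screen, 8.2 applies the exclusions at baseline, and medical history is taken at the consent visit, so some failures between consent and treatment are possible. A reader might infer that the two rates cannot both be right. The documents do not support that, because they never say that the 15 are lost after treatment starts. Chaining does not remove the inconsistency, however: 10.1 and 25.1 call 40 the number for analysis, and under chaining that number is 38.

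A reader might also infer that 15.2's analysed number fails at any enrolment, for instance by taking 27% off the 40 initial to leave 29 (about 75% power). No section plans 40 consented with that loss. On 10.1's own plan, 55 consented leaves 40 analysed, more than 38, with about 87% power; the gap between 40 and 38 is about 2 points, in the favourable direction.

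Two further replies have force. Much of the fall in power comes from the enrolment cut rather than the loss rate (Step 5). And 15.1 plans mixed-effects models on two sides of the same scalp, so the unpaired figures may be pessimistic. With r = 0.5, 80% is reached at 18 analysed. But 15.2 ignores the correlation, and no value is given on which to rely.

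**Conclusion.** The point holds in limited form, and 15.2 is wrong as written for the current enrolment. The meaning of 40 differs between 10.1/25.1 and 15.2, the 27% and 5% losses are not reconciled, and neither 40, 55 nor 38 is compatible with a maximum of 25. The 38 analysed cannot be reached at any loss rate.

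On 15.2's own basis, 20-25 enrolled gives 56-66% power at 5% loss and 46-53% at 27%, against the stated 80%. The choice of rate alone is worth about 10 to 13 points. These figures assume a two-sided test, effect 0.7 and no use of pairing. The 27% figures also assume that all 15 losses fall after enrolment. If some are failures at the consent visit that do not count as enrolled, the applicable loss is smaller than 27%; if 15.2's 5% is right for losses after the start, the upper figures apply. The documents do not allow a choice between them.

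**What to change.** 1. Align 10.1, 15.2 and 25.1 with the 20-25 in 5.1, and state for each number whether it means consented, started or analysed. Use 40, or its replacement, in one sense throughout.
2. Give the reason for the gap between consented and analysed, split into failures at the consent visit and losses after the first treatment.
3. In 15.2, apply the second of these rates to 20-25 and restate the analysed number with its power, or its detectable effect at 80% power. If the gap cannot be split, report both 5% (19-24 analysed, detectable effect 0.93-0.83) and 27% (15-18 analysed, 1.06-0.96) on the present unpaired basis.
4. State the sidedness of the test. If the paired design is to be credited, state the assumed correlation and show a range.

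The cost is wording in three sections and a short recalculation. No study procedure changes. The stated power becomes less favourable unless a correlation can be justified.
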